Appendix B. Phase II Schedule of Events

a. An Informed Consent/Assent for this study must be signed prior to initiating any study-related procedures.

b. The first visit during each week of treatment should occur on a Monday, with daily treatment sessions occurring on Monday through Friday of each week.

c. Subjects who prematurely discontinue should complete all Week 6 procedures within 2 days after their last TMS treatment session.

d. Efficacy, neuropsychological and safety assessments to be performed after last TMS treatment session on last day of the treatment week when assessments are required. YMRS to be completed if symptom indicating mania occurs. If positive, a M.I.N.I./M.I.N.I.-KID must be repeated to determine if subject meets full DSM-5 criteria for mania or hypomania. If positive, subject to be discontinued from the study and followed clinically.

- e. Performed on a subset of subjects at participating sites
- f. Adverse events occurring prior to randomization will be recorded as part of each subject's medical history. Those AEs occurring following the first TMS treatment session through 30 days after last study visit will be collected.
- g. Medication treatment for emergent insomnia and emergent anxiety is permitted (refer to protocol for usage allowance). Refer to Appendix D for the Concomitant Medication List.
- h. Motor Threshold Determination (MT) is to be performed prior to the administration of the first active TMS treatment session. In addition, MT may be repeated at any time during the course of the active TMS treatment sessions based on clinical assessment of the supervising physician. Justification for the additional MT must be documented and pre-approved by the Sponsor when possible.
- i. Taper occurs at end of acute treatment and prior to entry into Phase III.

Appendix	С.	Phase	Ш	Schedule of	f Events
11				, j	

Phase	6-Month Long-term follow up						
Timepoint	Month 1	Month 2	Month 3	Month 4	Month 5	Month 6/ET ^b	
Day(s)	Taper-30	Day 60	Day 90	Day 120	Day 150	Day 180	
Informed Consent/Assent	Xa						
Efficacy Assessments ^{c,h}							
HAMD ₂₄ /MADRS			x			x	
CDRS-R			x			x	
CGI-S	x	x	х	x	x	x	
QIDS-A17-SR	х	x	х	х	х	x	
Neuropsychological Assessments							
NIH Toolbox Cognition Battery						x	
Safety Assessments							
Vital Signs						x	
YMRS ^d							
C-SSRS [®]							
Structural MRI ^f						x	
Audiometry Assessment ^g						x	
Adverse Events ^{h,i}	X					Х	
Concomitant Treatment ^{h,j}	X					Х	
Motor Threshold Determination ^k							
TMS Retreatment ^{,c,,e,l} (5x/week for 6 weeks)							
See protocol text for description of retreatment parameters							

a. An Informed Consent/Assent for this study must be signed prior to initiating any study-related procedures.

b. Subjects who prematurely discontinue should complete all Month 6 procedures within 2 days after their last TMS treatment session.

c. TMS retreatments should begin on a Monday, with daily treatment sessions occurring on Monday through Friday of each week. All efficacy and safety assessments must be completed prior to the start of retreatment. Efficacy assessments must be completed every other week during each TMS retreatment with the assessment beings conducted after the last treatment for the two week block. TMS treatment to stop when the CGI-S value returns to the Phase III entry score or a full 6 weeks of TMS treatment has been completed. A 3 week taper should follow each retreatment session. TMS retreatment can occur multiple times if symptom re-emergence occurs.

- d. Y-MRS to be completed if symptom indicating mania occurs. If positive, a M.I.N.I./M.I.N.I. KID must be repeated to determine if subject meets full DSM-5 criteria for mania or hypomania. If positive, subject to be discontinued from the study and followed clinically.
- e. C-SSRS to be performed after last TMS retreatment session on last day of the retreatment week.
- f. Performed on a subset of subjects at participating sites.
- g. Audiometry assessments must be performed immediately prior to the start of the TMS retreatment and at the completion of the retreatment course.
- h. Efficacy assessments to be performed the end of each month for monthly visits. Subjects will be called to assess safety and well-being between visits at approximately 2 weeks post previous months visit.
- i. Those AEs occurring following informed consent signature through 30 days after the last study visit will be collected.
- j. Medication treatment for emergent insomnia and emergent anxiety is permitted (refer to protocol for usage allowance).
- k. A Motor Threshold Determination (MT) is to be performed prior to the administration of the first TMS treatment in each treatment course. In addition, motor threshold may be repeated at any time during the course of the active TMS treatment sessions based on clinical assessment of the supervising physician.
- I. TMS retreatment is to occur if the CGI-S increases by 1 from the score at entry into Phase III and is confirmed one week later.

Appendix D. Concomitant Medication List

CONCOMITANT MEDICATION LIST

This list should not be considered exhaustive. In general, drugs that are categorized into one of the drug categories listed in the table below should be treated similarly. Contact Neuronetics if questions arise.

CLASS: Drug	PRN	Chronic
ANTIASTHMA DRUGS		
Theo-Dur (theophylline)	N	Ν
Bronchodilators		
Alupent (metaproterenol), Proventil (albuterol), Ventolin (albutero	ol) Y	Y
Steroids		
Inhaled (Beclovent [beclomethasone], Azmacort [triamcinolone], Vanceril [beclomethasone])	Y	Y
Oral	С	N
Leukotriene antagonists		
Accolate (zafirlukast), Zyflo (zileuton), Singulair (monoleukast)	Ν	Y
ANTICOAGULANTS		
		Y
Coumadin (warfarin)	N	(w/ stable protime)
ANTICHOLINGERGICS		
Cogentin (benztropine), Artane (trihexyphenidyl), etc.	N	N
Phenylpropanolamine (PPA) and pseudoephedrine	N	N
	11	
ANTIHISTAMINE and DECONGESTANTS		
Sedating		
Anticholinergic (Benadryl [diphenhydramine], chlorpheniramine, brompheniramine, Atarax [hydroxyzine]) (not for psychiatric indica	ations) N	N
Non-sedating	,	
Allegra (fexofenadine), Claritin (loratadine), Zyrtec (cetirizine)	Y	Y
Hismanal (astemizole)	N	N
	•	
ANTI-INFECTIVE AGENTS		
Antibacterial antibiotics (Penicillin, sulfa, etc.)	Y	Y
Antifungal agents (ketoconazole, fluconazole, etc.)		
Topical creams and ointments	Y	Y
Oral antifungals (single-dose for vaginitis OK)	Y	N
Antiviral agents		
Zovirax (acyclovir), Famvir (famcyclovir), Valtrex (valacyclovir)	Y	Y
Antiretroviral drugs (e.g. AZT, protease inhibitors)	N	Ν
ANTI-NEOPLASTIC AGENTS	N	N
SKELETAL MUSCLE RELAXANTS		
Lioresal (baclofen), Flexeril (cyclobenzaprine), Parafon Forte	N	N

CLASS:	Drug	PRN	Chronic
	(chlorzoxazone), Robaxin (methocarbamol), Soma (carisoprodol)		
ANALGESI	CS AND ANTIPYRETICS		
	Nonsteroidal anti-inflammatory agents (aspirin, ibuprofen, naproxen)	Y	Y
	Opiate Agonists / Partial Agonists (including Ultram [tramadol])	Ν	N
	Miscellaneous analgesics & antipyretics (acetaminophen, paracetamol)	Y	Y
			1
CARE	DIOVASCULAR DRUGS (All drugs in this category must be stable for at lea	ast 3 mo	nths)
CARDIAC D	DRUGS		
	Calcium Channel Blockers for coronary disease or angina (see also "Antihypertensives") (Calan [verapamil], Cardizem [diltiazem], Norvasc [amlodipine], Procardia [nifedipine])	N	Y
Ar	ntiarrhythmics		
	Cordarone (amiodarone), lidocaine (note: local anesthesia injection OK), Mexitil (mexiletine), Norpace (disopyramide), Procan (procainamide), quinidine, Tambocor (flecainide)	N	N
	Digoxin (blood levels must be monitored)	Ν	Y
AN	TI-HYPERTENSIVE AGENTS (All anti-hypertensives must be stable dose	x 1 mon	ith)
	ACE Inhibitors (Vasotec, Capoten, Zestril)	Ν	Y
	Angiotensin receptor blockers (Cozaar)	Ν	Y
	Calcium Channel Blockers	Ν	Y
	Diuretics	Y	Y
	Phentolamine	Ν	Ν
Be	eta-Adrenergic Blockers (see also Anti-Migraine)		
	Low lipid solubility/CNS penetration (Corgard [nadolol], Tenormin [atenolol])	Y	Y
	High lipid solubility/CNS penetration (Inderal [propranolol], Lopressor [metaprotereno]), (low lipid solubility preferred)	Y	Y
Pe	eripherally-acting alpha adrenergic agents		1
	Cardura (doxazosin), Hytrin (terazosin), Minipress (prazosin)	Y	Y
Ce	entrally-acting alpha adrenergic agents		1
	Aldomet (methyldopa), Catapres (clonidine)	N	N
Al	I others (quanethidine, reserpine, etc.)	Ν	N
	Niacin (no slow-release preparations), Lipitor (atorvastatin), Lopid		
	(gemfibrozil), Mevacor (lovastatin), Zocor (simvastatin)	N	Y
VASODILA	TING AGENTS		
	Hydralazine	N	Y
	minoxidil (topical OK)	Ν	С
ANTI-CONV	/ULSANTS	Ν	N

	Drug	PRN	Chronic
РЅҮСНОТН	IERAPEUTIC AGENTS		
	Antidementia drugs (donepezil, etc.), Antidepressants, Antipsychotics	N	N
	(Thorazine, Prolixin, etc.), Miscellaneous Psychotherapeutic Agents		N
	nxiolytics (per protocol)	Y	N
Sti	imulants	Ν	
Se	datives and Hypnotics		
	Barbiturates, Benzodiazepines (except those allowed per the protocol),	Ν	Ν
	Other hypnotic agents		
	Ambien (zolpidem; per protocol), chloral hydrate (per protocol), Sonata (zaleplon; per protocol), Lunesta (eszopiclone; per protocol), Rozerem (ramelteon; per protocol)	Y	N
ANTIMANIC	AGENTS		
	Anticonvulsants, lithium	N	N
		11	
HORMONE	S & SYNTHETIC SUBSTITUTES		
	Corticosteroids (methylprednisolone, prednisone)	Y	С
	Mineralocorticoids (Florinef [fludrocortisone])	 	C
	Topical steroids (creams, ointments, eyedrops)	Y	Y
	pregnenolone	 	N
A n		N	N
All	drogens	N	N
C	DHEA, testosterone, danazol Intraceptives	IN	
	Hormonal (dose must be stable for at least 3 months): Oral, Vaginal		T
	Ring, Patch, Injections, Norplant (levonorgestrel)	Ν	Y
	Intrauterine device	Y	Y
	Latex condom, diaphragm and or cervical cap with spermicide	Ŷ	Ŷ
Fs	trogen replacement (postmenopausal, stable dose for \geq 3 months)	N	Ŷ
	yroid (stable dose for \geq 3 months and thyroid function tests within normal		
	its. Clinical significance to be determined by the physician)	Ν	Y
ANTIDIABE	TIC AGENTS		
	Oral hypoglycemic agents	Ν	Y
	Insulin's	Y	Y
DERMATOL	-OGIC AGENTS		
	Topical steroid preparations, Rogaine (topical minoxidil), Miscellaneous		N/
	creams, ointments, etc.	Y	Y
VITAMINS		Y	Y
		•	
OVER-THE-	COUNTER SUPPLEMENTS		
	chromium picolinate, DHEA, melatonin, pregnenolone, St. John's Wort	Ν	Ν

S: Drug	PRN	Chro
ROINTESTINAL DRUGS		
Cisapride (propulsid)	Y	Y
Antiemetics		
Over-the-counter (e.g., Emetrol [dextrose], Coke syrup)	Y	Y
Phenothiazines & related drugs (Compazine [prochloroperazine],		
Phenergan [promethazine], Reglan [metoclopramide], Tigan	С	N
[trimethobenzamide]), Anzemet (dolasetron), Kytril (granisetron), Zofran	-	
(ondansetron)	N	
Marinol (dronabinol),	IN	N
Antacids		
AlternaGel (aluminum hydroxide), Amphojel (aluminum hydroxide), Basaljel (aluminum carbonate), Bicitra (sodium citrate), Maalox (calcium		
carbonate), MagOX (magnesium oxide), Mylanta (magnesium	Y	Y
hydroxide), Tums (calcium carbonate), UroMag (magnesium oxide)		
Antidiarrhea agents		1
Arco-Lase (trizyme), Furoxone (furazolidone), Motofen (difenoxin),	N	
Sandostatin (octreotide acetate)	N	N
Imodium (loperamide), Lomotil (diphenoxylate), Pepto-Bismol (bismuth	Y	N
subsalicylate)	•	
Cathartics & Laxatives		
Colace (docusate), enemas, Metamucil, Perdiem, Senokot, Soflax,	Y	Y
Unifibre Dialaga (daguagta)	v	
Dialose (docusate)	Y	Y
Antisecretory agents	NI	
H2 Blockers	N Y	N Y
Axid (nizatidine), Pepcid (famotidine), Zantac (ranitidine)	T	
Proton pump inhibitors	Y	Y
Prevacid (lansoprazole), Prilosec (omeprazole)	T	1
Miscellaneous gastrointestinal drugs	v	
Carafate (sucralfate)	Y)
Reglan (metoclopramide)	N	N
Levsin (L-hyoscyamine sulfate)	Y	Y
MIGRAINE		
DHE 45 (dihydroergotamine), Imitrex (sumatriptan), methysergide,		
Midrin (isometheptene mucate), Zomig (zolmitriptan)	Ν	C
Fiorinal (butalbital, ASA, caffeine), Cafergot (ergotamine)	Y	C
Nonsteroidal anti-inflammatory drugs (ibuprofen, naproxen, Toradol,		
etc.)	Y	۱
Beta-blocking drugs		1
Corgard (nadolol), Tenormin (atenolol), Other beta-blockers (e.g.,	v	Y
Inderal [propranolol])	Y	1
& MUCOUS MEMBRANE AGENTS	Y	Y

MISCELLANEOUS DRUGS Acutane, All over-the-counter diet pills, Ionamin (phentermine resin), Lioresal (baclofen), Wellbutrin (bupropion), Zyban (bupropion) Allopurinol, colchicine		
Lioresal (baclofen), Wellbutrin (bupropion), Zyban (bupropion) Allopurinol, colchicine	,	
	1	Ν
	r	Y
Fosamax (alendronate)	1	Y
Gold compounds, hydroxychloroquine, and methotrexate for severe arthritis	1	С
Smoking cessation aids (Nicorrette, nicotine patches)	;	С
Chantix (varenicline)	1	Ν

ENDNOTES

N = Never to be used in this study.

Y = Can be used in this study for either PRN or Chronic use as indicated in the table.

C = Call for Sponsor approval. Approval for these medications is generally granted if the patient is otherwise acceptable, including stable medical condition, no undue risk, no other "marginal" considerations in the medical history or concomitant medications. Or may be used during the long-term maintenance phase with certain restrictions.

## Section 1. Study Design and Objectives

For a more complete description of the study protocol, please refer to the current version of the protocol, entitled, 44-02219-000, "A Randomized, Sham-Controlled Trial Evaluating the Safety and Effectiveness of NeuroStar Transcranial Magnetic Stimulation (TMS) Therapy in Depressed Adolescents, version C.

#### A. Trial Design Summary:

Study 44-02219-000 is a multi-center, randomized, sham-controlled clinical trial evaluating the safety and effectiveness of treatment with the NeuroStar TMS Therapy system in adolescent patients ages 12 through 21 who have failed to received treatment benefit from prior administration of antidepressant medications. The study is organized into 3 separate phases. During Phase I, patients meeting inclusion and exclusion criteria are randomly assigned in a 1:1 ratio to receive either daily treatment with the NeuroStar TMS Therapy device in the XPLOR research configuration or sham NeuroStar treatment for up to 6 weeks (30 treatments). Patients who do not meet criteria for clinically significant treatment benefit are offered the opportunity to enter Phase II, where open-label active NeuroStar TMS Therapy is provided to all patients for up to 6 weeks (30 treatments). Patients who receive clinically significant treatment benefit at the conclusion of either Phase I or Phase II are offered the opportunity to proceed into Phase III, where NeuroStar TMS Therapy is tapered, and patients are continually monitored for up to 6 months to determine the durability of effect of benefit from the acute treatment phases of the study. All patients are treated with NeuroStar TMS Therapy as a monotherapy, no antidepressant medications are permitted during the course of all three study Phases. During Phase III, patients are permitted to receive a reintroduction of an acute course of NeuroStar TMS Therapy if they meet protocol-defined criteria for symptom re-emergence.

## **B.** Primary Study Objective:

• To evaluate the antidepressant effects of daily, active TMS (when compared with sham treatment) in adolescents meeting criteria for Major Depressive Disorder, single or recurrent episode (Phase I).

#### C. Secondary Study Objectives:

- To evaluate the acute and long-term safety of TMS treatment in adolescent MDD subjects.
- To evaluate the durability of benefit of TMS treatment over the course of 6 months in subjects who received clinical benefit from acute treatment course(s) (Phase III).
- To evaluate the benefit of daily, active, open-label TMS in Phase I subjects who did not receive protocol-defined clinical benefit; as new acute treatment (sham to active) or as extended treatment course (blinded active to open label active) (Phase II)

## Section 2. Statistical Justifications

#### A. Sample Size Justification:

There are no large, randomized controlled trials of the use of transcranial magnetic stimulation (TMS) in the treatment of adolescent major depressive disorder that can be used to estimate effect size. Therefore, several different sources of evidence were used to estimate the expected effect size of treatment as proposed in this

44-02219-204, Rev C 21-JAN-2019

Page 3 of 28

protocol. First, evidence was reviewed from the study by Wall and colleagues, who reported preliminary data from a small patient population of adolescents treated with the NeuroStar TMS Therapy System in an open label study design (Wall, 2011). This study is especially relevant because it is the only available evidence using the specific TMS device (i.e., the NeuroStar TMS Therapy System) that will be utilized in the NeuroStar TMS Adolescent MDD RCT, and it used the identical stimulation parameters and duration of treatment proposed in this study protocol. In that report, eight adolescent patients participated who had previously failed to benefit from treatment with 2 or more antidepressant medications and were currently in stable treatment with a single ineffective (selective serotonin reuptake inhibitor, SSRI) antidepressant medication. Seven of 8 patients, ages 14-18 years, completed all 30 treatments in this study. The primary outcome measure was the Children's Depression Rating Scale-Revised (CDRS-R) which showed significant improvement from baseline (mean [SD]) (69.6 [6.6]) at treatment 10 (50.9 [12]), P<0.02, treatment 20 (40.1 [14]), P<0.01, treatment 30 (32.6 [7.3]), P<0.0001, and at 6-month follow up (32.7 [3.8]), P<0.0001.

Using this data, the mean change in CDRS-R total score was estimated to be approximately 33, with a standard deviation of 7.3. It is presumed that a treatment difference of 8.0 points on the CDRS-R scale between randomized treatment conditions may be anticipated in a sham-controlled study, and that a conservative estimate for a pooled standard deviation is 10.0 points, which results in an estimated standardized effect size of 0.80. This is considered to be the upper bound of an expected magnitude of treatment benefit in an adolescent depression study population. Under these assumptions, it is presumed that a sample size of approximately N=35 patients per treatment group, with an alpha level = 0.05 would provide approximately 90% power to detect a treatment difference between active and sham TMS groups.

Another important source of evidence to consider in estimating an effect size for this study can be derived from randomized controlled trial evidence from the study of antidepressant medications that are FDA approved as treatments for adolescent patients with major depressive disorder. The relevant medications to consider include the medications fluoxetine (Emslie, et al., 1997; 2002) and escitalopram (Emslie, et al., 2007). Replicated studies of the antidepressant fluoxetine have shown active versus sham treatment differences using the CDRS-R that range from approximately 7 to 9 points, with associated pooled standard deviations of approximately 9 to 12 points. Estimated standardized effect sizes in these studies are reported as moderately large, approximately 0.50 (Emslie, et al., 1997; 2002). Results of similarly designed studies of escitalopram suggest a lower estimated standardized effect size of approximately 0.30 (Emslie, et al., 2009).

In addition to these data, the results of a large, federally-supported multisite study of the use of antidepressant medication for the treatment of adolescent major depression are also relevant to consider. This study was not specifically directed at the question of antidepressant medication monotherapy alone, rather the design was intended to examine the effectiveness of the combination of antidepressant medication with cognitive-behavior therapy (CBT). Nevertheless, examination of the medication alone treatment condition in this study provides important supportive information in an estimation of the anticipated standardized effect size in adolescents. The Treatment of Adolescent Depression Study (TADS) (March, et al., 2004) examined the benefit of the use of fluoxetine alone, CBT alone, or the combination of the two versus a placebo condition. In that report, the use of fluoxetine alone versus placebo was observed to demonstrate a standardized effect size of 0.68, similar in magnitude to the results of the Emslie and colleagues studies described above (Emslie, et al, 1997; 2002). It should be noted, however, that these studies with antidepressant medication utilized a treatment-naïve study population, excluding patients with treatment resistant depression.

Based on the aggregate evidence described here, it is anticipated that this study, if effective in demonstrating the superiority of NeuroStar TMS Therapy® compared to sham TMS in adolescent patients with treatment resistant major depressive disorder, may be expected to demonstrate a standardized effect size of approximately 0.50 to 0.60. As a stand-alone analysis, it is therefore expected that a sample size of 50 patients per treatment arm, at an alpha level of 0.05, should provide greater than 85% power to detect a statistically significant difference between the treatment groups. However, as noted further below, efficacy also may be established by analysis of the adolescent study data using a frequentist approach which borrows data from two prior adult RCTs in major depression using the NeuroStar TMS Therapy System.

44-02219-204, Rev C 21-JAN-2019

Page 4 of 28

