The primary outcome measure was remission using the HAMD24 (HAMD24 total score ≤ 3 or 2 consecutive HAMD24 total scores <10) through 6 weeks of acute treatment. A statistically significant benefit of active TMS as compared to sham treatment for the HAMD24 remission outcome (Active TMS: 13.4% vs Sham TMS: 5.0%, P=0. 0173) was observed in the ITT study population (N=197). An adjusted odds ratio of achieving remission with active TMS was 4.05 (95% confidence interval (CI), 1.28-12.83) as compared to sham TMS. The baseline to endpoint change score outcome using the HAMD24 also favored active TMS compared to sham treatment (-2.11, 95% CI: -4.30, 0.08; P=0.0588). Baseline to endpoint outcomes for patients treated with active TMS were statistically significant as compared to sham treatment as measured using the MADRS (P=0.0136), CGI-S (P=0.0181) and the patient-rated IDS-SR (P=0.0008). For the categorical endpoints, higher rates of remission were observed for patients receiving active TMS as compared to sham treatment as measured using the MADRS (P=0.0170) and the patientrated IDS-SR (P=0.1199), and for response (50% improvement from baseline) for all three measures (HAMD24, P=0.0104; MADRS, P=0.0063; IDS-SR, P=0.0145). Standardized effect size estimates for the continuous outcome endpoints range from 0.43 to 0.67, indicating a moderate to large effect size in this patient population. Study 101 evaluated the safety and efficacy of NeuroStar TMS Therapy in 301 adult outpatients across 23 sites with moderate to severe major depressive disorder and who failed to benefit from 1 through 4 prior antidepressant medication trials administered at an adequate dose and duration, and verified using the ATHF (O'Reardon2007; Janicak, 2008). The patient population was similar to patients enrolled in the independent NIMH-funded trial. Outcome on the primary efficacy endpoint (MADRS change from baseline at 4 weeks) favored NeuroStar TMS Therapy (P=0.057) over sham treatment for the ATHF 1 through 4 population. A subgroup analysis of the overall study population demonstrated that the device was safe and effective for patients who had failed to achieve satisfactory improvement from one prior antidepressant medication (N=164 patients, P=0.0006, MADRS, primary efficacy endpoint) in the current episode.

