As noted elsewhere in this protocol, the sites will remain blinded to which efficacy measure has been declared as the primary outcome and to the point of efficacy declaration in order to improve the study's signal detection ability. Point of declaration and the primary outcome measure will be documented in the study master file prior to unblinding of the dataset. The null hypothesis will be tested in an analysis of covariance of the LV, using baseline score, and ATR medication resistance level as fixed effect covariates, adjusting for site differences using a random effect. As discussed elsewhere, the ATR medication resistance levels will group subjects categorically by number of medications which have shown an adequate degree of resistance for that subject. These resistance levels will be grouped into two categories in statistical model, 0-1 in the current episode or 2-4 in the current episode, unless the final distribution of ATR scores in the study population suggests another allocation would be more statistically appropriate. All tests are two-sided, at the 5% level. The primary outcome should be available and meaningful for nearly all subjects, so the main analysis will be by strict intention-to-treat as defined above. An analysis of observed cases only will be performed as a secondary outcome measure. A site by treatment interaction analysis will be done as a secondary analysis to see if there is significant heterogeneity in the effect of TMS across sites. In particular, we will examine site-specific treatment effects (with confidence intervals) to test for evidence of true reversal of effect.

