The null hypothesis will be tested in an analysis of covariance of the LV (value from 6-week visit unless it is missing, then LOCF used), using baseline score, and ATR medication resistance level as fixed effect covariates, adjusting for site differences using a random effect. As discussed elsewhere, the ATR medication resistance levels will group subjects categorically by number of medications which have shown an adequate degree of resistance for that subject. These resistance levels will be grouped into two categories in statistical model, 0-1 in the current episode or 2-4 in the current episode, unless the final distribution of ATR scores in the study population suggests another allocation would be more statistically appropriate. All tests are two-sided, at the 5% level. The primary outcome should be available and meaningful for nearly all subjects, so the main analysis will be by strict intention-to-treat as defined above. An analysis of observed cases only will be performed as a secondary outcome measure. A site by treatment interaction analysis will be done as a secondary analysis to see if there is significant heterogeneity in the effect of TMS across sites. In particular, we will examine site-specific treatment effects (with confidence intervals) to test for evidence of true reversal of effect.

Secondary outcomes include other continuous measures, and within-subject dichotomous variables as outlined in the efficacy variables described elsewhere in this protocol. The treatment effect null hypothesis will be tested by logistic regression on treatment group assignment with adjustment for site and ATR medication resistance level. In addition, the longitudinal symptom scores will be analyzed with a general linear model adjusting for baseline scores and ATR medication resistance level, using a saturated means model for time since baseline, with treatment effect parameterized by a linear effect in time. The correlation of scores within individuals over time will be handled by allowing a within-subjects residual covariance matrix selected by exploration of the sample semi-variogram, as described by Diggle, Liang and Zeger. If this exploration reveals that a mixed model approach will fit the covariance structure better, random effects will be included in the model. As in the main analysis, site by treatment interactions will be tested.

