#### **D.** Flow of Analysis:

First, the adolescent study data will be analyzed standing alone. If the results of the analysis of the adolescent study shows a statistically significant treatment group difference in favor of the active treatment at a pre-specified alpha level = 0.05, then this study alone will be sufficient to establish efficacy in the adolescent population. If the stand alone analysis does not have statistically significant results, the meta-analysis will be performed.

Based on this meta-analysis, there are 3 essential criteria to declare success and conclude that the evidence rejects the null hypothesis of no difference between active TMS and sham TMS in adolescent patients with treatment resistant major depressive disorder. These criteria are:

- 1) The main effect of treatment on the primary efficacy variable of mean change from baseline on the HAMD24 in the adolescent/adult studies meta-analysis will be statistically significant, and fall below the specified alpha level of 0.05,
- 2) There will be no statistically significant evidence of interaction between Study and Treatment on the primary efficacy outcome variable at the pre-specified alpha level  $\geq 0.10$ ,
- 3) The study-specific treatment effect observed for the primary efficacy outcome variable in the adolescent study as a stand-alone analysis will reside between the ranges of 1.7 points to 5.5 points on the HAMD24, and to meet the maximum Type I error rate of 15%.

The criteria above are clinically justified based on the results using the HAMD24 outcome measure in the prior adult studies which ranges from 1.7 to 2.5 (O'Reardon, et al, 2007; George, et al, 2010). The maximum Type I error rate of 15% for the adolescent data alone is justified given the large dataset available in adults (N=491) and that adult and adolescent populations should respond similarly to TMS Therapy. Simulations using data from the adult studies and N=100 adolescents, shows that with a type I error rate of 5%, the observed HAMD24 mean difference between active and sham treatment would need to be 2.67, which would require a result greater than what it would need to achieve had it been considered alone. For this reason, the 15% type I error rate for the adolescent data is justified.

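### The stated stand-alone power of more than 85% with 50 per arm does not hold across the plan's own effect range of 0.50 to 0.60; unadjusted, it is about 70% to 84%

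*SAP*

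**What the plan says.** SAP Section 2.A and Protocol 15.1 carry the same argument. After reviewing a small open-label adolescent study and trials of antidepressant medication, they conclude that the trial, if successful, "may be expected to demonstrate a standardized effect size of approximately 0.50 to 0.60". The next sentence draws the consequence for the adolescent study analysed alone: "a sample size of 50 patients per treatment arm, at an alpha level of 0.05, should provide greater than 85% power". No single effect within the range is tied to that figure, and neither a baseline correlation nor a dropout rate is mentioned.

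The test is described in Protocol 15.2 and SAP Section 2.B. On sidedness: "All tests are two-sided, at the 5% level". The model is an analysis of covariance "using baseline score, and ATR medication resistance level as fixed effect covariates", with a random effect for site.

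The same section contains a second power statement, for an effect of 8.0/10.0 = 0.80: "a sample size of approximately N=35 patients per treatment group, with an alpha level = 0.05 would provide approximately 90% power".

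SAP Section 2.D then fixes the order of analysis. The adolescent data are tested alone first. "If the stand alone analysis does not have statistically significant results, the meta-analysis will be performed".

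**The concern.** The power sentence is presented as following from the whole range 0.50 to 0.60. Fifty per arm is a familiar size, and at an effect of 0.50 it is well known to fall clearly short of 80% power in a two-sided 5% comparison of means. A claim of more than 85% over that range therefore needed checking.

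More than a line of background text is at stake. Under the SAP's order of analysis, failure of the stand-alone test opens the route that borrows the adult data. On that route the adolescent data alone need only meet a maximum Type I error rate of 15%. One minus the stand-alone power is the chance that the trial needs this route even though the assumed effect is real. A reader judging how far the trial depends on adult data would take that chance to be below 15%.

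**Working it through.** **Inputs.** n = 50 per arm, 1:1 allocation (Protocol study summary; SAP 1.A and 2.A). Two-sided alpha 0.05 (Protocol 15.2; SAP 2.B). Standardised effect d = 0.50 to 0.60, midpoint 0.55 (SAP 2.A; Protocol 15.1). All patients are taken as evaluable, because no loss rate is given.

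**Formula.** For two means, the noncentrality is λ = d√(n/2). Normal approximation: power ≈ Φ(λ − 1.96). Exact: the probability that a noncentral t with 2n − 2 degrees of freedom and noncentrality λ falls outside the two-sided 5% critical values.

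**Step 1: the plan's companion figure.** With n = 35 and d = 0.80, λ = 0.80 × √17.5 = 3.347. The normal approximation gives Φ(1.387) = 91.7% and the exact t gives 91.0%. Both agree with the stated value of about 90%, so a simple unadjusted two-sided calculation reproduces the plan's other power statement.

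**Step 2: the stand-alone figure.** With n = 50, √(n/2) = 5 and df = 98.

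| d | λ | Normal approx. | Exact t | 1 − power (t) |
|---|---|---|---|---|
| 0.50 | 2.50 | Φ(0.54) = 70.5% | 69.7% | 30.3% |
| 0.55 | 2.75 | Φ(0.79) = 78.5% | 77.7% | 22.3% |
| 0.60 | 3.00 | Φ(1.04) = 85.1% | 84.4% | 15.6% |

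The effect needed for exactly 85% is 0.605 by t, or 0.599 by normal approximation. The size needed for 85% by t is 73, 61 and 51 per arm at 0.50, 0.55 and 0.60.

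**Step 3: could a different reading rescue the claim?**

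- *One-sided 5%.* The t-test gives 79.9%, 86.1% and 90.9%. This contradicts the two-sided rule and still fails at 0.50.
- *Baseline adjustment.* If 0.50 to 0.60 is on the unadjusted SD scale and ρ is the baseline-to-endpoint correlation, λ becomes d√(n/2)/√(1 − ρ²), taken here with 96 df. The documents give no ρ, so these values are assumptions:

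| Assumed ρ | d = 0.50 | d = 0.55 | d = 0.60 |
|---|---|---|---|
| 0.3 | 73.7% | 81.4% | 87.6% |
| 0.5 | 81.5% | 88.2% | 92.9% |
| ρ needed for 85% | 0.56 | 0.42 | 0.13 |

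- *Loss of patients.* Protocol 11.5 says withdrawn subjects are not replaced. If 10% contributed no outcome (an assumption; 45 per arm), unadjusted power would be about 65%, 73% and 80%. This moves the figures further from 85%.

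**Context only.** Protocol 8.1 says of one adult trial: "Standardized effect size estimates for the continuous outcome endpoints range from 0.43 to 0.67". With 50 per arm those effects give 57% and 91%. They span several outcomes and are not the stated basis of the 0.50 to 0.60 assumption, so nothing here depends on them.

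**The case against.** Four points deserve a fair hearing.

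First, the figure is reachable at the top of the range: by normal approximation, 0.60 gives 85.1%. That is correct, and at 0.60 the whole gap is a matter of t against z. The companion check cannot show which of the two was used, since both fit about 90%. What remains wrong is that a best-case figure is attached to a range. At 0.55 and 0.50 the choice of method moves power by less than one point, while the exact-t shortfalls are about 7 and 15 points.

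Second, the planned test is an analysis of covariance, not an unadjusted comparison. This is the stronger objection, because a correlation of 0.5 would bring 0.55 and 0.60 above 85%. It would still leave 0.50 at 81.5%. The plan neither states a correlation nor says that the 85% relies on one, and its companion figure reproduces without adjustment. Adjustment is a possible basis for a higher claim, but not one the documents supply.

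Third, the practical effect is limited. The plan is open about its sample-sparing intent and mentions borrowing straight after the power sentence. No test, threshold or sample size depends on the figure, and the SAP is a January 2019 revision that describes some conduct in the past tense. This limits the severity but does not make the sentence right.

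Fourth, the consequence for borrowing rests on the SAP's order of analysis. Protocol 15.2 puts it the other way round, with the adolescent study standing alone if the pooling criteria fail. The fallback percentages therefore apply to the SAP's sequence. The power figures do not depend on the order.

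**Conclusion.** The concern holds. On the plan's own inputs, 50 per arm does not give more than 85% power over the effect range to which the claim is attached. Unadjusted, two-sided and with everyone evaluable, power runs from about 70% to 84%, and 85% is reached only at the very top, by normal approximation. Under the SAP's sequence, the chance of needing the adult data despite a true effect is about 30%, 22% and 16% at 0.50, 0.55 and 0.60, against an implied maximum of 15%. At the lower end that is a factor of two.

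The conclusion rests on the documents' n, alpha, sidedness and effect range. It could be softened only by a baseline correlation that the plan does not give. It is a repeated misstatement of a core design figure that should be corrected, but it does not invalidate the planned analysis.

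**What to change.** In SAP Section 2.A and Protocol 15.1, replace the power sentence with one that covers the range, for example: *Fifty patients per arm give about 70%, 78% and 84% power at standardised effects of 0.50, 0.55 and 0.60 (two-sided alpha 0.05, unadjusted comparison, all patients evaluable).* If a higher figure is to be claimed because of baseline adjustment, state the assumed baseline-to-endpoint correlation, its source, and the effect size to which the figure applies.

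The cost is wording in two places, and a stated power that looks less favourable. The sample size, test and conduct do not change.

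A separate check in the same section: the plan says "the mean change in CDRS-R total score was estimated to be approximately 33, with a standard deviation of 7.3". The open-label results it has just reported give a baseline mean of 69.6 and a treatment-30 score of 32.6 with SD 7.3, so the difference in means is 69.6 − 32.6 = 37.0. The quoted change and SD look like the endpoint score and its SD, and should be verified against the source. This does not affect the power figures above.
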